5.4 Tumor Characteristics

Tumor characteristics will include, but are not limited to:

- Histology of primary cancer
- Proof of metastases
- Location of the index tumor
- Size of the index tumor

6 STUDY TREATMENTS

6.1 Cryoablation Treatment

For cryoablation in the palliation of painful bone metastases, subject preparation, anesthesia, intra-operative monitoring, and postoperative management are identical to those of standard cryoablation routinely performed at all clinical centers participating in this study.

6.2 Subject Enrollment

To minimize selection bias within the enrolled subject population, participation in the study is to be offered to all eligible patients on a consecutive basis as they present to the physician at the site. Each study site will maintain a screening log to include minimal health information regarding each non-enrolling patient (e.g., sex, age, reason for not enrolling, etc.). As the non-enrolled patients will not sign an informed consent form the data collected will not include personally identifiable information (as defined in 45 CFR 164.514).

Patients who wish to participate in this study and sign a written informed consent form will be considered to be enrolled in the study and will be assigned a unique subject identifier number to be used throughout the study.

6.3 Subject Withdrawal

Subjects may withdraw from this study at any time, with or without a reason, without prejudice to further treatment. Investigators should make every effort within the bounds of safety and subject choice to have each subject complete the study. If a subject does not return for a scheduled visit, every effort should be made to contact the subject. In any circumstance, every effort should be made to document the subject's outcome, if possible. The investigator should inquire about the reason for withdrawal; request the subject return for a final visit, if applicable and follow-up with the subject regarding any unresolved adverse events. As possible, the reason(s) for withdrawal (if given) will be recorded.

If the subject withdraws from the study and also withdraws consent for disclosure of future information, no further evaluations should be performed for the study and no additional data should be collected. The sponsor may retain and continue to use any data collected before such withdrawal of consent.

6.4 Risks

Potential risks of bone tumor cryoablation in the intraoperative/early postoperative period include bleeding, infection, fracture, nerve injury, skin injury (burn/frostbite) and injury to adjacent tissues or organs.

Potential delayed risks of cryoablation include complications that may lead to death. A list of anticipated adverse events may be found under Appendix B. There may be unforeseen complications, and other complications may occur in the location of the tumor treated by cryoablation.

6.5 Potential Benefits

Cryoablation is an FDA-cleared treatment modality for the ablation of cancerous or malignant tissue and benign tumors, and palliative intervention. Potential benefits of cryoablation for the palliation of painful bone metastasis include the reduction of pain and the reduction of pain medication. Other benefits may include a reduction in other treatment methods for pain control.

6.6 Study Supplies

Study sites will use Galil Medical's commercially available Visual-ICE Cryoablation System and needles labeled for use for this study. A Regulatory Documents binder will be provided to each site. Questionnaires, subject instructions and applicable worksheets will also be provided to each site, if applicable. The study monitor should be contacted for any issues related to these study supplies. Cryoablation needles are supplied in single use, sterilized packages. Once opened, they should be used immediately for the current procedure or discarded. Store cryoablation needles according to the recommendations on the commercial packaging.

6.7 Pain Medications and Non-drug Therapies

Pain medication use, specifically opioid medications and non-steroidal anti-inflammatory drugs (NSAID), both prescription and over the counter (OTC) shall be documented. Detailed specifics with regards to medication name, dose, frequency, and reason will be collected regarding pain medication usage at the time of screening and throughout the study. The total medication used

in the immediate 24 hours prior to the visit will be recorded. In the event of death or the subject is lost to follow up, the last known 24 hour period intake of opioid or NSAID medication will be collected if known. Opioid medications will be converted to morphine equivalent doses for comparison and evaluation purposes.⁴³ See Appendix E for Instructions for Morphine Equivalent Daily Dose (MEDD) conversion.

Supplemental treatment which, in the investigator's opinion, becomes necessary during the course of the study must not be denied to the subject. If this supplemental treatment is described as a therapy expressly not permitted, the subject's participation in the study may need to be discontinued due to non-permitted concurrent therapy. Please refer to section 8.4 for information on specific supplemental treatments for this protocol.

7 SUBJECT POPULATION

7.1 Subject Selection

This study can fulfill its objectives only if appropriate subjects are enrolled. The following eligibility criteria are designed to select subjects for whom cryoablation therapy is considered appropriate. All relevant medical and non-medical conditions should be taken into consideration when deciding whether cryoablation therapy is suitable for a particular subject.

7.2 Inclusion Criteria

Eligible subjects for this study must meet all of the following criteria:

- 7.2.1 18 years of age or older
- 7.2.2 Metastatic disease involving bone with metastatic disease previously confirmed by prior biopsy;
or
Metastatic disease involving bone previously confirmed on imaging (e.g. CT or MRI) with known (biopsied) primary disease (primary bone cancer is excluded)
- 7.2.3 Current analgesic therapies have failed, the subject is not a candidate for, OR the subject is not experiencing adequate pain relief from current pain therapies (e.g. radiation, analgesics)
- 7.2.4 The 'worst pain' in the last 24 hours must be reported to be 4 or above on a scale of 0 (no pain) to 10 (pain as bad as subject can imagine)
- 7.2.5 Pain must be from one painful metastatic lesion involving the bone that is amenable to cryoablation with CT (additional less painful metastatic sites may be present)
- 7.2.6 Cryoablation should be performed within 14 days of screening visit
- 7.2.7 If taking hormonal therapy, use should be stable (no changes within 4 weeks prior to the cryoablation procedure)
- 7.2.8 Karnofsky Performance Status (KPS) score ≥ 60
- 7.2.9 Life expectancy ≥ 3 months
- 7.2.10 No debilitating medical or psychiatric illness that would preclude giving informed consent or receiving optimal treatment and follow-up
- 7.2.11 Known coagulopathy or bleeding disorders are controlled

7.3 Exclusion Criteria

Subjects not eligible for participation in this study include those who have any of the following:

- 7.3.1 Primary cancer is leukemia, lymphoma, or myeloma
- 7.3.2 Tumor involves a weight-bearing long bone of the lower extremity with the tumor causing > 50% loss of cortical bone
- 7.3.3 Has undergone prior surgery at the tumor site or the index tumor has undergone previous surgery or ablation treatment
- 7.3.4 Prior radiation therapy of the index tumor <3 weeks prior to the screening visit
- 7.3.5 Index tumor causing clinical or radiographic evidence of spinal cord or cauda equina compression/effacement
- 7.3.6 Anticipated treatment of the index tumor that would require iceball formation within 0.5 cm of the spinal cord, brain, other critical nerve structure, large abdominal vessel (possibly achieved with additional maneuvers such as hydrodissection)
- 7.3.7 Index tumor involves the skull
- 7.3.8 Currently pregnant, nursing, or wishing to become pregnant during the study
- 7.3.9 Serious medical illness, including any of the following: uncontrolled congestive heart failure, uncontrolled angina, myocardial infarction, cerebrovascular event within 6 months prior to the screening visit
- 7.3.10 Concurrent participation in other studies that could affect the primary endpoint

8 STUDY PROCEDURES

The study schedule of events and the specific procedures performed at each visit are shown in Table 1, Schedule of Events. Each subject will undergo a total of 9 visits, including a screening visit, the procedure visit, 7 post-operative visits. In the event the subject is not able to return for office follow up visits, the follow up assessment may be conducted via telephone. More visits may be required if medically necessary.

The remainder of this page is intentionally blank

Table 1: Schedule of Study Events

Procedures	Screening	Baseline Assessment ^b (within 24 hrs of cryo)	Procedure ^a	W 1 ^d ±5 days	W 4 ^d ± 12 days	W 8 ^d ± 12 days	W 12 ^d ± 12 days	W 16 ^d ± 12 days	W 20 ^d ± 12 days	W 24 ^{d,e} ± 12 days
Informed Consent	X									
Inclusion/Exclusion	X									
Medical Comorbidities	X									
Targeted Medical History	X									
Demographics	X									
Pain Medication Assessment	X ^c	X		X	X	X	X	X	X	X
KPS	X ^c	X		X	X	X	X	X	X	X
BPI-SF Question #3	X ^c									
BPI-SF		X		X	X	X	X	X	X	X
Tumor characteristics			X							
Cryoablation Procedure			X							
Safety Assessments			X	X	X	X	X	X	X	X

^a The procedure is recommended to be performed within 14 days of the screening visit.

^b The Baseline Assessment should be completed within 24 hours prior to the cryoablation procedure. Evaluation of the inclusion/exclusion criteria should be re-evaluated prior to the cryoablation procedure to ensure criteria are met.

^c In the event the screening visit is completed within 24 hours of the cryoablation procedure, a separate BPI-SF #3 is not required. Complete the BPI-SF, KPS, and Pain Medication Assessment per the Baseline Assessment requirement.

^d In the event a subject is unable to return for a scheduled office visit follow up, the visit may be conducted via telephone.

^e Week 24/Study Completion or Early Termination

8.1 Screening

The screening period begins after informed consent has been obtained. The screening visit allows the investigator to assess a subject's eligibility for this study. Medical records from prior to the signed informed consent date may be used to confirm eligibility.

The following assessments will be collected:

- BPI- Question 3 only (worst pain in last 24 hours)
- KPS
- Comorbidities
- Demography
- Targeted medical history
- Review inclusion/exclusion criteria
- Documentation of pain medication (opioid and/or NSAID) and reason for use

8.2 Baseline

The following items will be completed within 24 hours prior to the cryoablation procedure and will serve as baseline information for all applicable protocol directed evaluations.

- BPI Questionnaire
- KPS
- Documentation of pain medication (opioid and/or NSAID) and reason for use

8.3 Cryoablation Procedure

Pre-procedure labs may be performed per institutional standard of care. It is recommended the cryoablation be performed within 14 days of the screening visit. Extension beyond this timeframe may be necessary since this is a chronically ill population.

Typically, two freeze-thaw cycles will be used. The cryoablation needles will use compressed argon gas through the Joule-Thomson effect to produce extremely low temperatures within the target tumor(s). Antibiotics (per site standard of care) may be given at the investigator's discretion.

The following data will be collected at the time of the procedure or prior to discharge, as applicable:

- Tumor location and description
- Tumor size measured by two methods:
 - 3-dimensional measurements (cm) and
 - Greatest trans-axial diameter (cm)
- Number and type of cryoablation needles used
- Freeze and thaw times, per cycle
- Estimation of % tumor ablation during procedure
- Concomitant procedures

- Number and type of intraoperative complication(s)
 - Severity of complication(s)
- Duration of hospital admittance/stay
- Safety assessments

8.3.1 Cryoablation Needle Testing

Before anesthesia inducement of the subject, all cryoablation needles should be tested in accordance with the Galil Medical cryoablation system User Manual to confirm their freezing function and structural integrity.

8.3.2 Cryoablation Needle Placement

A Galil Medical cryoablation system will be used per the manufacturer's guidelines. Galil Medical's cryoablation needles will be placed using image guidance in a pattern necessary to fully freeze the target tumor. Image-guided ablation of bone metastases may be performed under general anesthesia or moderate sedation.

8.3.3 Freezing Procedure

Once freezing has been initiated, the cryoablation procedure will be monitored with imaging to visualize iceball growth, to ensure the ablation zone is adequately frozen and adjacent anatomical structures are protected. As the freezing continues, the ice formations from each of the cryoablation needles coalesce so the targeted portions of the ablation zone are frozen. Throughout the phases of the procedure, the ablation zone should be monitored under imaging guidance at intervals deemed appropriate by the investigator. Typically when the leading edge of the ice has reached at least 5 mm beyond the tumor periphery, the freezing process should be stopped. Typically, two freeze-thaw cycles should be utilized. Freeze and thaw cycle times may vary depending on the size and iceball coverage of the tumor and proximity to adjacent critical structures. Passive or active thaw should be carried out between freeze cycles. Following the last freeze cycle, a brief active thaw should be utilized prior to attempting to remove the needle(s).

The low-density changes within the tissue should be measured to approximate the size of the ablated region. Hemodynamic monitoring should be done in compliance with national and local standards.

8.4 Recurrent Tumor Pain/New Tumor Pain

Additional targeted therapies (cryoablation, RFA, MWA, HIFU, radiation, surgery, etc.) are not permitted on an index tumor per this protocol. If the investigator feels additional targeted therapy is appropriate, the subject will be discontinued from the study.

If a new painful tumor is identified during the follow-up period, targeted therapies (cryoablation, RFA, MWA, HIFU, radiation, surgery, etc.) are permitted, provided that the region of identifiable pain may be clearly distinguished from the region/tumor treated during the initial cryoablation procedure.

Other therapies, including pain medications and chemotherapy are permitted.

8.5 Weeks 1, 4, 8, 12, 16, 20, and 24 Post-Procedure Follow-up

In the event that a subject cannot return for an office visit, the subjects should be contacted by telephone. Subjects will be assessed at the above intervals to complete the following assessments:

- BPI
- Pain medication (opioid and/or NSAID) and reason for use in the prior 24 hours prior to the visit
- KPS
- Additional new bone metastases
- Overall tumor burden
- Any additional therapies the subject may have started for bone metastases (index tumor or new metastases)
- Safety Assessment

8.6 Study Completion or Early Termination

The 24 week visit will be the final visit for subjects undergoing a single cryoablation procedure. Subjects who request Early Termination from the study will be asked to return for a final visit to complete the above assessments if possible.

Subjects may be considered "lost to follow-up" after 3 unsuccessful attempts to contact the subject with one contact being a registered letter to the last known address of the subject. Site should document all attempts to contact the subject in the source documents.

9 ASSESSMENTS

9.1 Demography

Demographic information will be collected from the subject during the screening visit. The information will consist of age at the time of enrollment, race, ethnicity and gender.

9.2 Targeted Medical History

Targeted medical history information must be obtained from each subject entering the study. Obtaining accurate medical history is necessary to ensure documented baseline health status and to ensure that subjects meet study entry criteria.

9.3 Biopsy

A biopsy of a tumor(s) in the bone(s) metastasized from another primary disease may be obtained at the discretion of the treating investigator per his/her standard practice.

9.4 Pain Scale and Quality of Life

The Brief Pain Inventory (BPI) Short Form is a standardized scale for consistently capturing patient reported symptom assessments. This two-page form uses numerical rating scales to measure both pain severity and the resulting functional interference caused by pain. The BPI provides a list of descriptors to help the patients

report the pain. Subjects rate the pain at its "worst," "least," and "average" in the last 24 hours, as well as "now," using a numerical rating scale that ranges from 0 (no pain) to 10 (pain as bad as you can imagine). Subjects rate the amount of interference from pain on a scale of 0 (does not interfere) to 10 (completely interferes) regarding the following areas: general activity, mood, walking ability, normal work, relations with other people, sleep, and enjoyment of life.⁴⁴ See Appendix C.

Although this is a subjective measure, it is determined to be the most appropriate tool to use for the outcome measures. The treatment goal in subjects with painful bone metastases is usually palliative pain control. Since the objective of this study is not focusing on treating/curing the bone metastases or the original tumor source, this scale is relevant in assessing the outcome.

9.5 Physical Performance

Physical function assessments will be measured using the standardized scale from the Karnofsky Performance Status (KPS). The KPS is a standard way of measuring the ability of cancer patients to perform ordinary tasks. The scores range from 0 to 100. A higher score means the patient is better able to carry out daily activities. KPS may be used to determine a patient's prognosis, to measure changes in a patient's ability to function. (See Appendix D)

9.6 Self-assessed Overall Treatment Effect (OTE)

Overall treatment effect will be assessed based on the subject's opinion of the effect (better, same, worse) the cryoablation procedure has had on their well-being. The subject will be asked to compare their well-being at each follow up visit compared to the previous visit or telephone call.

9.7 Imaging

As outlined in this protocol, all subjects will have an initial confirmation of metastases involving bone using CT, MRI, or US prior to cryoablation. The cryoablation procedure will be completed under imaging guidance. Follow-up imaging is at the discretion of the investigator.

10 ENGINEERING, MANUFACTURING, HANDLING AND ACCOUNTABILITY

10.1 Manufacturing, Packaging and Labeling

The Galil Medical cryoablation system and needles are manufactured, packaged and labeled according to current Good Manufacturing Practices (cGMP) and applicable international, national and local regulations, laws, and guidelines.

10.2 Handling and Storage

The Galil Medical cryoablation system and needles, necessary equipment, and disposables are handled and stored according to Galil Medical's specifications.

10.3 Recall of Device

The Galil Medical cryoablation system is designed and built in accordance to IEC 60601-1, 3rd edition standard performance and safety specifications for surgical medical instruments. Any recall of the system will be done in accordance with applicable international, national and local legislation and guidelines, as well as the sponsor's requirements.

11 STATISTICAL ANALYSIS

11.1 General Methods

This is a prospective, single-arm study designed to evaluate the effectiveness, durability, and safety of Galil Medical's cryoablation system and needles for the palliative treatment of metastatic tumors involving bone.

11.2 Sample Size

A 2 point reduction from baseline in worst pain score is considered to be clinically meaningful. The expected device performance is at least a 3.2 point reduction from baseline in mean worst pain score and the expected standard deviation is 2.7. With these assumptions, PASS 13 software was used to compute a sample size for a one-sample T-test with superiority by a margin:

A sample size of 42 achieves 80% power to detect superiority using a one-sided t-test when the margin of superiority is -2.0 and the true difference between the mean and the reference value is -3.2. The data are drawn from a single population with a standard deviation of 2.7. The significance level (alpha) of the test is 0.025.

With an attrition rate at 8-weeks estimated to be 30%, the total treated study sample size will be approximately **60 subjects**, with continued enrollment until at least 42 evaluable subjects have reached 8 weeks. This sample size will be considered clinically sufficient to give indications of device effectiveness.

11.3 Missing Data

Missing data will be prospectively minimized through training of the participating investigator and site staff, and through appropriate clinical trial management. Every effort will be made to collect all data points in the study. All subject data that is available on subjects who drop out during the course of the study will be included where possible.

Sensitivity analyses will be performed on the primary efficacy endpoint using two methods of missing data imputation: multiple imputation and last observation carry forward.

11.4 Analysis Populations

Intent-to-Treat (ITT) analyses will be performed on all subjects with a Galil Medical cryoablation system as the attempted treatment. Endpoints will also be evaluated using per protocol population (PP).

11.4.1 General Analysis

Data will be analyzed using descriptive statistics. Continuous variables (e.g., age) will be summarized by the number of subjects, mean, standard deviation, median, interquartile range, minimum and maximum. Categorical variables (e.g., race) will be summarized by frequencies and percentages of subjects in each category.

11.4.2 Primary Efficacy Endpoint

The endpoint for this study will be measured as follows: assessment of the effectiveness of cryoablation associated with palliation of pain in subjects with metastatic lesions involving bone by measuring the average difference of pre- and post-treatment worst pain in 24 hours from baseline to 8 week follow-up interval as measured Brief Pain Inventory (BPI) scale. A mean difference of 2 points reduction is considered clinically significant.

Calculations:

- 8-Week follow-up minus baseline worst pain will be calculated for each subject.
- Mean change over all subjects will be calculated.
- The mean reduction in pain at 8-weeks will be evaluated for clinical meaning

To be considered clinically meaningful the 95% confidence interval's upper bound on the mean reduction in worst pain score must be less than -2.

Subjects without missing endpoint data will be considered completers. Intent-to-Treat Completers (ITTC) analysis as well as Per-Protocol Completers (PPC) analysis will be supplemented by missing data sensitivity analyses. Sensitivity analyses will be performed on the primary efficacy endpoint using two methods of missing data imputation: multiple imputation and last observation carry forward. These imputation methods will be employed on both the ITT and PP populations resulting two additional outcome analyses: Intent-to-Treat Imputed (ITTI) and Per-Protocol Imputed (PPI). Of the four analyses, the primary hypothesis test will be considered the ITTI analysis with multiple imputation.

11.4.3 Safety Endpoints

The safety endpoint for this study is to assess the incidence and severity of intraoperative events, post-operative adverse events, serious adverse events and unanticipated adverse device effects.

Point estimates and two-sided Exact 95% confidence intervals will be generated for procedural related events in the following categories:

- Intra-operative events
- Post-operative adverse events
- Serious adverse events
- Unanticipated adverse device effects

The safety analysis will be performed on the per-protocol population. No formal statistical hypothesis testing will be performed for safety endpoints.

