5.2 Safety Endpoints

The safety endpoint for this study is to assess the incidence and severity of procedure or device-related adverse events.

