Intent-to-Treat (ITT) analyses will be performed on all subjects with a Galil Medical cryoablation system as the attempted treatment. Endpoints will also be evaluated using per protocol population (PP).

Efficacy Endpoint Analysis

Primary Efficacy Endpoint

The primary endpoint for this study will be measured as follows: improvement in self-reported pain scores defined by ≥ 2 point reduction in worst pain in the last 24 hours using the Brief Pain Inventory (BPI) from baseline to 8 weeks. A mean difference of 2 points reduction is considered clinically significant.

Analysis Methods

Pain assessments using the BPI will be made by examining the average difference of pre- and post-treatment worst pain in 24 hours at week 8 follow-up as measured on the Brief Pain Inventory (BPI) scale. A mean pain reduction of 2 points from baseline in worst pain score is considered clinically meaningful.

Calculations:

- 8-Week follow-up minus baseline worst pain will be calculated for each subject.
- Mean change over all subjects will be calculated.

- The mean reduction in pain at 8-weeks will be evaluated for clinical meaning.

To be considered clinically meaningful the 95% confidence interval's upper bound on the mean reduction in worst pain score must be less than -2.

Subjects without missing endpoint data will be considered completers. Intent-to-Treat Completers (ITTC) analysis as well as Per-Protocol Completers (PPC) analysis will be supplemented by missing data sensitivity analyses. Sensitivity analyses will be performed on the primary efficacy endpoint using two methods of missing data imputation: multiple imputation and last observation carry forward. These imputation methods will be employed on both the ITT and PP populations resulting two additional outcome analyses: Intent-to-Treat Imputed (ITI) and Per-Protocol Imputed (PPI). Of the four analyses, the primary hypothesis test will be considered the ITI analysis with multiple imputation.

For any complete case analysis, the subjects missing BPI at week 8 would be excluded from the analysis. For any imputed analysis, the subjects missing BPI at week 8 would use the imputed week 8 value to determine if the responder threshold was met for that subject.

The multiple imputation model will consider the BPI score at each time point (BPI at 1, 4, 12, 16, 20, and 24 weeks will be part of analyses) in addition to age and gender.

Safety Endpoint Analysis

Safety Endpoint

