Demographics, disease status, labs, procedural information, and protocol deviations will be assessed by mean, standard deviation, median, interquartile range, minimum and maximum for continuous measures, and frequencies and percentages of patients in each category for categorical measures. These measures include, but may not be limited to:

Demographics

- Age
- Gender
- Race and ethnicity
- Height, weight, and BMI
- Comorbidities
- Smoking history
- Karnofsky Performance Status

Disease Status

- Biopsy information
- Primary cancer diagnosis
- Treatment/therapy information
- Tumor location

Procedural Information

- Tumor location and description
- Tumor size measured by two methods:
 - 3-dimensional measurements (cm) and
 - Greatest trans-axial diameter (cm)
- Number and type of cryoablation needles used
- Number of freeze and thaw cycles
- Freeze and thaw times, per cycle
- Estimation of % tumor ablation during procedure
- Concomitant procedures
- Number and type of intraoperative complication(s)
 - Severity of complication(s)
- Duration of hospital stay
- Safety assessments

All protocol deviations

Subject Disposition

Subject disposition will be presented as:

- Number of subjects enrolled
- Number of subjects completing each follow-up visit
- Number of subjects withdrawn or lost to follow-up
- Number of subject deaths
- Number of subjects evaluable for ITT and PP analyses

Randomization and Blinding

As this is a single arm study, no randomization or blinding will be performed. To minimize selection bias within the enrolled patient population, participation in the study is to be offered to all eligible patients on a consecutive basis as they present to the physician at the site.

Handling of Missing Data

Missing data will be prospectively minimized through training of the participating investigator and site staff, and through appropriate clinical trial management. Every effort will be made to collect all data points in the study. All patient data that is available on patients who drop out during the course of the study will be included where possible.

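### Safety rates are to be computed on a per-protocol population that neither document defines, so treated subjects and their related events can drop out of the reported risk.

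*Protocol*

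**What the plan says.** Protocol 5.2 sets the safety objective: "The safety endpoint for this study is to assess the incidence and severity of procedure or device-related adverse events". Protocol 11.4.3 gives the estimator: "Point estimates and two-sided Exact 95% confidence intervals will be generated for procedural related events in the following categories". The categories are intra-operative events, post-operative adverse events, serious adverse events and unanticipated adverse device effects. There is no hypothesis test for safety. The population is then fixed: "The safety analysis will be performed on the per-protocol population". The SAP, under Safety Endpoint Analysis, repeats both the estimator and the population.

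On populations, Protocol 11.4 says: "Intent-to-Treat (ITT) analyses will be performed on all subjects with a Galil Medical cryoablation system as the attempted treatment". Both it and the SAP's Analysis Populations section then only name the second set; in the SAP's words, "Endpoints will also be evaluated using per protocol population (PP". No criteria follow in either place.

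The remaining mentions add no membership rule. Protocol 11.4.2 says "These imputation methods will be employed on both the ITT and PP populations", and the SAP's Subject Disposition section asks for "Number of subjects evaluable for ITT and PP analyses".

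**The concern.** A safety analysis should count every subject exposed to the procedure. A PP set, as the term is ordinarily used, removes subjects for eligibility failures or protocol deviations, and in an ablation study those can be the subjects most likely to be harmed. This is inference, because the documents do not define PP, but the text shows how it could happen:

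- Protocol 7.3 excludes certain cortical bone loss, cord compression and iceball formation close to the cord or critical nerves. A subject treated despite one of these would be a typical PP exclusion. Protocol 6.4 lists fracture and nerve injury among the risks.
- Protocol 21 allows deviations made to remove an immediate hazard. A subject with such a deviation could leave the safety table because of it.
- The ITT set covers attempted treatment. An aborted procedure could fall outside PP, yet intra-operative events are the first category to be reported.

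The study is single-arm and unblinded, and Protocol 12.2 foresees periodic interim analyses that include adverse event assessments. No time is set for fixing PP membership, so nothing prevents it being decided with events in view.

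Protocol 3.3 says the data are meant to support a labelling expansion, and the SAP calls the study pivotal. With no safety test planned, these rates and intervals are the formal safety result.

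**Working it through.** **1. The natural denominator.** The documents give no figure for the safety analysis, so start from the treated sample size. Inputs from Protocol 11.2 and the SAP's Sample Size Justification: expected change -3.2, margin -2.0, SD 2.7, one-sided alpha 0.025, 30% attrition. The distance is 3.2 - 2.0 = 1.2. A one-sample t-test (noncentral t) has power 0.793 at n = 41 and 0.803 at n = 42, so 42 evaluable subjects is reproduced. Then 42 / (1 - 0.30) = 60 treated. An all-treated safety analysis would have a denominator of about 60.

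**2. Is PP the same as ITT, or defined indirectly?** No.

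- ITT has a rule (attempted treatment). PP has none in Protocol 11.4 or in the SAP's Analysis Populations.
- The two are run as separate efficacy analyses and counted separately in disposition.
- The completer rule, "Subjects without missing endpoint data will be considered completers", is applied on top of both ITT and PP. It separates PP completers from PP; it does not say who is in PP.

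**3. What exclusions can do to the reported rate.** All counts here are assumptions. The formula is x/n with the Clopper-Pearson 95% interval, where the lower limit is the 2.5% point of Beta(x, n - x + 1) and the upper limit is the 97.5% point of Beta(x + 1, n - x).

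All treated, 3 subjects with an event in 60: 5.0% (1.0 to 13.9%).

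| Event subjects among those excluded | 5 excluded (n = 55) | 10 excluded (n = 50) |
|---|---|---|
| 0 | 3/55 = 5.5% (1.1 to 15.1%) | 3/50 = 6.0% (1.3 to 16.6%) |
| 1 | 2/55 = 3.6% (0.4 to 12.5%) | 2/50 = 4.0% (0.5 to 13.7%) |
| 2 | 1/55 = 1.8% (0.05 to 9.7%) | 1/50 = 2.0% (0.05 to 10.6%) |
| 3 | 0/55 = 0% (upper limit 6.5%) | 0/50 = 0% (upper limit 7.1%) |

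A second set of assumed counts shows the same pattern. With 6/60 = 10.0% (3.8 to 20.5%) and 6 subjects excluded, the PP rate is 6/54 = 11.1% (4.2 to 22.6%) if no event subject is excluded, 3/54 = 5.6% (1.2 to 15.4%) if three are, and 0/54 = 0% (upper limit 6.6%) if all six are.

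**4. How likely are these rows if exclusion has nothing to do with events?** With 3 event subjects in 60, the chance that at least one is excluded is 1 - (55 × 54 × 53)/(60 × 59 × 58) = 1 - 157,410/205,320 = 23.3% with 5 excluded, and 1 - (50 × 49 × 48)/(60 × 59 × 58) = 1 - 117,600/205,320 = 42.7% with 10. The chance that all three are excluded is 10/34,220 = 0.03% and 120/34,220 = 0.35% respectively. If exclusion is linked to harm, all these probabilities rise by an unknown amount.

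**The case against.** Five points can fairly be made for the plan.

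- **The general clause may cover safety.** The populations section describes ITT analyses and says endpoints will also be evaluated on PP. Safety is an endpoint, so read literally both sets apply. But the safety section names one population, and the specific sentence would normally govern. At best the clauses conflict, and an all-treated safety analysis is not assured.
- **Attrition need not shrink PP.** Missing week-8 data is handled by the completer label, and Protocol 14 limits recorded events to 30 days after the procedure. The planned 30% attrition is therefore not a reason to expect a much smaller safety set. This stands: the exposure is exclusion for eligibility or deviations, in unknown number.
- **Events are captured regardless.** Protocol 14 records and reports related events without reference to PP, Protocol 17 provides a Medical Monitor, and the SAP summarises intraoperative complications, deaths and all deviations. Omitted subjects could probably be detected. That is real but partial mitigation, because none of it sets the numerator or denominator of the planned rates and intervals.
- **The size is assumed, and the 0% rows are extreme.** Both are true. The documents' own background figures are sparse and cover higher-grade events only: one possibly related Grade 3 event among 28 pilot subjects and one major complication in 61 patients.
- **Nothing is tested, and all-treated rates can be produced later.** This is correct, but it only shows that the change is easy. Without a test, the estimates are the safety result.

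**Conclusion.** The concern holds. Both documents assign the safety estimates to a population that is separate from the attempted-treatment set and has no membership rule, so a faithful analysis can leave exposed subjects and their related events out of the study's only safety endpoint.

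That the stated population is wrong for safety is clear from the text. The size and direction of any effect are not. They depend on how many treated subjects PP excludes and whether those subjects had events, and the documents give neither. The rate rises slightly if no excluded subject had an event and falls otherwise. With about 60 treated subjects and few events, one or two excluded event subjects are enough to move the estimate materially: from 5.0% to 3.6% or 1.8% in the 5-excluded illustration. The point should be corrected before the safety data are analysed.

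**What to change.** In Protocol 11.4.3 and in the SAP's Safety Endpoint Analysis, replace the population sentence with: The safety analysis will be performed on all subjects in whom cryoablation was attempted (the ITT population). Any PP safety table should be labelled supplementary. Because the documents do not say when an attempt begins, the same edit should state this, so that aborted procedures are counted consistently.

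Since PP efficacy analyses remain in the plan, it would also be sensible to write a PP membership rule into Protocol 11.4 and the SAP before outcome data are analysed. The safety correction does not depend on that.

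The cost is one sentence in each document plus short definitions. No new data are needed, and the primary efficacy test is untouched because it already uses the ITT set with multiple imputation. The reported safety rates may turn out less favourable, or slightly more favourable, than PP rates would have been.
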